The Participant Interview Form will be completed by the investigator after questioning the participant. This will provide a baseline for tinnitus, dizziness, medications and other relevant information.

Counseling

Along with the pre-implant candidacy evaluation and pre-implant study testing, participants will be seen by the surgeon and audiologist at their CI center for routine, clinical visits that occur prior to CI surgery. These visits will include discussions regarding the risks of CI surgery as well as performance outcomes with a CI to assure appropriate expectations.

Spouse/Significant Other – Pre-Implant Questionnaires

CPHI

The CPHI will be completed by the participant's spouse/significant other and will provide a baseline measure of the participant's communication in everyday life from the perspective of the spouse/significant other.

HII-SOP

The HII-SOP will be completed by the participant's spouse/significant other. The HII-SOP will provide a baseline of the perceived impact of the participant's hearing loss on the participant's spouse/significant other.

Surgery

Participants will be implanted with their selected CI device. The surgical procedure for implantation of each device will be according to each device's current approved labeling. Each surgeon will determine the length of participants' hospital stay based on their recovery. The following data will be obtained: date of surgery, device specifics and adverse event information.

Initial Stimulation of the Cochlear Implant

The initial stimulation of the CI will take place 2-4 weeks after surgery based on the surgeon's recommendation. Programming of each participant's CI speech processor will be performed according to each center's typical CI programming schedule. Selection of programming parameters will be determined by each center's routine, clinical procedures for optimizing CI recipient performance. At this visit the following will be obtained:

Unaided Audiometric Threshold Levels*

Air conduction thresholds using insert earphones will be obtained for each ear at 250, 500, 1000, 2000, 3000, 4000, 6000 and 8000 Hz. Masking will be used when appropriate.

*If pre-implant, unaided audiometric testing reveals no response at each frequency in the poor ear, unaided audiometric testing in that ear does not need to be completed at this or any of the post-implant test sessions.

Participant Interview Form

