An IRB approved investigator will be responsible for obtaining informed consent for each participant prior to initiating any study procedures. The consent process will include informing each participant of the study purpose, possible risks and potential benefits. These include the normal risks associated with general anesthesia, as well as other risks such as facial paralysis, dizziness, meningitis, postoperative discomfort, and flap complications. Potential participants will be given ample time to read the informed consent. Potential participants will be able to take the informed consent home to read and discuss study participation with friends and family. Individuals will be encouraged to ask questions. Once all questions are answered, both the participant and the investigator obtaining informed consent will sign and date the consent form. The original signed and dated form will be kept with the participant study records and a copy given to the participant.

Confidentiality

In accordance with Good Clinical Practices and with the Health Insurance Portability and Accountability Act of 1996 (HIPAA), all information concerning study participants will be treated as confidential by all persons involved in the study. Each investigational site will follow the requirements of the site's IRB regarding confidentiality.

Data generated for the study will be stored in a limited-access file area and accessible only to study site research team members, the Sponsor, and FDA/relevant health authorities/regulatory agencies. All reports and communications with the Sponsor relating to study participants will identify participants only by a unique participant identification code. Full participant identification will be kept by the investigators at each investigational site.

Protocol Amendments

Protocol modifications that impact participant safety or study validity will be approved by the FDA prior to implementation. In addition, modifications will be documented in written form and approved by each investigational site's IRB prior to implementation. In the case of a medical emergency, to remove immediate apparent hazard to participants, a change may be made, preferably after discussion with the Sponsor. In these instances, the IRB and FDA will be notified as soon as possible.

Data Management

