- Copies of all case report forms submitted to the Sponsor.
- Site Delegation Signature Log.

All study-related records must be maintained for at least two years after study closure. The Sponsor will notify investigators at each site when records are no longer needed. The investigator will not discard any records without notifying the Sponsor.

Study Report and Publication

Neither the complete nor any part of the results of the study carried out under this protocol, or any of the information provided by the sponsor site for the purposes of performing the study, will be published or passed on to any third party without the consent of the Sponsor (via the study Principal Investigator, [name]). Any investigator involved with this study is obligated to provide the Sponsor with complete test results and all data derived from the study.

At completion of the study, the compiled data will be analyzed and results shared with investigators from the investigational sites. Likewise prior to publication of results, the investigators from the investigational sites will be provided a copy of the accepted publication manuscript.

Adverse Events

Adverse Event (AE)

An AE is any unexpected medical occurrence or worsening of a pre-existing medical condition following implantation and exposure to the device, regardless of whether the AE is related to the surgery or device.

Adverse events (AEs) that occur during this study may be associated with the CI surgery, including AEs from general anesthesia, or specifically associated with the device use. An AE will be deemed device-related when, in the judgment of the study site's Primary Investigator, there is a logical connection between the device use and the event, above and beyond the study procedure itself.

Serious Adverse Event (SAE)

A SAE is any unexpected medical occurrence which:

- Results in death
- Is life-threatening
- Requires in-patient hospitalization for more than 24 hours or prolongation of hospitalization which is not specifically required by the protocol
- Results in permanent impairment of a body function or permanent damage to a body structure
- Requires medical or surgical intervention to preclude permanent impairment of a body function or permanent damage to a body structure

Unanticipated Adverse Device Effect (UADE)

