A UADE is "any serious adverse effect on health or safety or any life-threatening problem or death caused by, or associated with, a device, if that effect, problem, or death was not previously identified in nature, severity, or degree of incidence in the investigational plan or application (including a supplementary plan or application), or any other unanticipated serious problem associated with a device that relates to the rights, safety, or welfare of subjects." [FDA 21 CFR 812.3(s)]

Investigator Responsibilities

Throughout the course of the study, all efforts will be made to remain alert to possible AEs. Of primary concern will be the participant's safety and providing appropriate medical care. Detailed information regarding AEs will be recorded by the study site at

the time an AE occurs using the “*Adverse Event CRF*”. All AEs will be recorded from the day of enrollment to the time when the participant exits the study or to study termination, whichever is the last, even if the event was acknowledged as a risk factor in the Informed Consent.

AEs will be recorded on the “*Adverse Event CRF*” and will include the following information:

- Date of onset
- Date reported to the clinic
- Description of the AE
- Seriousness (yes or no)
- Investigator’s assessment of the relationship of the AE to the device
- Investigator’s assessment of the relationship of the AE to the procedure
- Treatment
- Outcome
- Relationship to device, implantation procedure and/or underlying disease

A UADE will be reported directly to the study site’s IRB and the Sponsor within 10 working days of learning of the event or as dictated by the study site’s IRB, whichever is sooner. Information regarding the UADE will be recorded on the “*Unanticipated Adverse Device Effect CRF*”.

Adverse Event Follow-up – Investigator Responsibilities

All AEs must be followed until resolution. The study site will follow-up as necessary with the participant to explain as well as possible the reason for and nature of the AE. This may include additional tests or consultation with other health care professionals. The Sponsor may request that the study site perform additional specific evaluations. AE follow-up information, as needed, will be recorded using a “*Previously Reported AE or UADE Follow-Up CRF*”.

Adverse Event Follow-up – Sponsor Responsibilities

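### The AE and SAE definitions require an unexpected event, but the recording rule keeps consented risks and starts at enrollment, so sites could count and grade known surgical risks differently

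*Combined protocol and SAP*

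**What the plan says.** All references are to the combined protocol and SAP.

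- **Adverse Event (AE):** "An AE is any unexpected medical occurrence or worsening of a pre-existing medical condition following implantation and exposure to the device", whether or not it is related to the surgery or device. The next paragraph adds: "Adverse events (AEs) that occur during this study may be associated with the CI surgery, including AEs from general anesthesia".
- **Serious Adverse Event (SAE):** "A SAE is any unexpected medical occurrence which" meets one of five outcome criteria, permanent impairment of a body function among them. This definition has no timing words.
- **Investigator Responsibilities:** "All AEs will be recorded from the day of enrollment to the time when the participant exits the study" or to study termination, "even if the event was acknowledged as a risk factor in the Informed Consent". The AE form carries a yes/no item for seriousness.
- **Informed Consent Process:** participants are told of the usual anesthesia risks and of "facial paralysis, dizziness, meningitis, postoperative discomfort, and flap complications".
- **Surgery:** "The following data will be obtained: date of surgery, device specifics and adverse event information".
- **Initial Stimulation of the Cochlear Implant:** this visit falls 2-4 weeks after surgery.
- **Safety:** the evaluation rests on the count, kind and degree of all AEs. Events up to 6 months post-implant are summarized, among other things, by severity or seriousness. No hypothesis is tested, and no start date for the summary is given.

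The protocol does not define the word unexpected and gives no list of expected events. The UADE definition deals separately with whether an event was previously identified.

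**The concern.** The recording rule applies to AEs, and the AE definition decides what an AE is. If the definition excludes something the rule says must be recorded, each site has to choose which text to follow. The conflict arises on two points: whether an event already known as a risk counts, and when counting starts.

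Safety is a secondary objective, and the AE records are its only source. The same records go to the DSMB and into the annual report to the FDA. The protocol also states that surgical risk in this population is no greater than in cochlear implantation generally. The known surgical risks are the events that bear on that statement, so their count and their seriousness grade should not depend on which paragraph one of the three or four sites applies.

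**Working it through.** The plan gives no safety figure to reproduce. The check is a comparison of the texts, followed by a small illustration of scale.

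**1. Expectedness, AE level.** The definition asks for an unexpected occurrence, or the worsening of a pre-existing condition; the second limb can be read as needing no unexpectedness. The recording rule keeps events disclosed at consent. On the ordinary meaning of the word, a complication described to the participant beforehand is not unexpected, so the definition removes what the rule retains. The AE section is also at odds with itself, because it accepts anesthesia events and anesthesia risks are among those disclosed.

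**2. Expectedness, SAE level.** The clause that keeps consented risks governs the recording of AEs. No matching clause exists for seriousness. Take a facial paralysis that becomes permanent:
- Recording rule: logged as an AE, although disclosed at consent.
- Outcome criterion for an SAE (permanent impairment): met.
- Opening condition of the SAE definition (unexpected): not met on a literal reading.
- Seriousness item on the form: could be answered no.
- Safety summary by severity or seriousness: carries that answer.

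**3. Start of collection.** An event between enrollment and surgery falls in the recording window but outside the AE definition. The definition also joins implantation with exposure to the device and does not say whether exposure begins at surgery or at first stimulation 2-4 weeks later. On the later reading, peri-operative events fall outside it, against the AE section's own sentence on surgical and anesthesia events and against the collection of AE data at surgery.

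**4. Scale.** The only input from the documents is the number of participants, 37 to 40 (Participant Population). One participant whose SAE is misclassified moves the observed proportion by 1/40 = 2.5% to 1/37 = 2.7%. This is arithmetic on the denominator, not an estimate of how many events would be affected.

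The documents give no rate for any known surgical risk, so the rates *p* below are assumptions. Expected affected participants = 37*p*; chance of at least one = 1 − (1 − *p*)^37.

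| Assumed *p* | Expected among 37 | Chance of at least one |
|---|---|---|
| 1% | 0.4 | 31% |
| 5% | 1.9 | 85% |
| 10% | 3.7 | 98% |
| 20% | 7.4 | 99.97% |

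In the extreme case that every such event were left out or downgraded, the table would show 0/37. The exact one-sided 95% upper bound would be 1 − 0.05^(1/37) = 7.8% (0/40: 7.2%), which would wrongly exclude a true rate of 10%. The plan does not commit to such a bound. The line shows only how a reader might use a zero count.

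**The case against.** The strongest reply is that the intent is plain and several provisions serve it. The recording rule deals with consented risks by name. The AE section accepts surgical and anesthesia events, so unexpected can hardly mean not listed in the consent form. AE information is collected at surgery. The Participant Interview Form asks about dizziness and the implant site at initial stimulation and at each post-implant visit, to help identify AEs. Every recorded AE gets a seriousness entry, the sponsor checks the forms for inconsistencies, and the DSMB reviews adverse events. The safety analysis is descriptive, and the primary efficacy analysis is untouched.

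Most of this stands, and it makes wholesale loss of surgical events unlikely. It does not close the SAE gap: a seriousness item helps only if the definition behind it is sound, and the only definition given keeps the unexpectedness condition. Nor does it settle the start date.

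A reader might infer more than the text supports:
- *That the SAE definition is also limited to the period after implantation.* It has no timing words.
- *That the passages disagree on when recording ends.* The AE definition gives no end date, so there is nothing to disagree with.
- *That the pre-surgery window is at most 4 months.* Candidacy Determination lets surgery take place later, with parts of the evaluation repeated.
- *That none of the listed risks can ever be an SAE.* That follows only if unexpected is taken to mean not disclosed at consent, which the protocol never says.

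**Conclusion.** The inconsistency is real. On expectedness, both definitions conflict with the recording rule, and for SAEs nothing brings known risks back in. On timing, only the AE definition conflicts with recording from enrollment, and the meaning of device exposure is left open. The consequence is possible inconsistent counting or grading between sites, not a demonstrated loss of events. It would affect a descriptive secondary objective and leaves the CNC and sound-field analyses, the sample size and the power unchanged.

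The size is 2.5 to 2.7 percentage points for each participant whose SAE is misclassified. How many would be affected cannot be derived from the documents. The conclusion assumes that at least one site reads unexpected in its ordinary sense. The passages should be reconciled before the safety data are summarized, but this does not rank among the points on which the trial's main result depends.

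**What to change.** 1. Delete the unexpectedness condition from the AE and SAE definitions. Keep anticipation only in the UADE definition.
2. In the AE definition, replace the limit to the time after implantation and device exposure with a start at enrollment, to match Investigator Responsibilities. This also removes the question of when exposure begins.
3. In the Safety section, state the date from which the 6-month summary counts events. Use the onset date already recorded on the AE form to tabulate events before surgery separately from those after it, so that pre-surgery events do not blur the implant-related picture.

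The cost is a change of wording in the protocol and the form instructions. A few more events will be logged, and the AE and SAE counts may look slightly less favourable. No new data item or visit is needed.

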In summary, many hearing-impaired patients function with noticeable hearing asymmetry. When hearing is asymmetric and the loss in the poor ear is moderate-to-profound, lack of treatment for that ear is very common, which results in monaural hearing. Listening with just one ear, particularly a hearing-impaired ear, is detrimental to signal segregation and communication. Individuals with asymmetric hearing loss frequently seek medical care due to pervasive communication difficulties. The only available treatment that can provide hearing to the deaf ear is a CI. At this time, individuals with asymmetric hearing loss are not routinely implanted in the poor hearing ear simply because the contralateral, better hearing ear has hearing loss in the moderate range rather than the severe to profound range. A prospective, single-arm, multi-center clinical trial is critically needed to address the deficits of patients with asymmetric hearing loss and explore potential treatment with a CI. Outcomes from this study will also inform a future pivotal clinical trial.

Study Objectives

Primary Objective: Obtain preliminary efficacy data in adults with asymmetric hearing loss who receive a cochlear implant (CI) in the poor hearing ear and maintain a hearing aid (HA) in the better hearing ear. Efficacy is defined as post-implant improvement in the poor ear with a CI compared to pre-implant with a HA. Measures are sound field threshold levels and CNC monosyllabic words in quiet.

Secondary Objectives:

1. Obtain efficacy data related to bimodal hearing. Efficacy is defined as post-implant improvement (CI in poor ear + HA in better ear) compared to the pre-implant best-aided condition (either HAs in both ears, or a HA in the better ear alone for adults with no aidable hearing in the poor ear). Measures are sound localization, speech recognition in noise, speech recognition at soft presentation levels, perceived hearing handicap, and reported quality of life.
2. Evaluate safety associated with cochlear implantation in individuals with asymmetric hearing loss. The safety evaluation will be based on the number, type and degree of all adverse events.
3. Collect essential preliminary information related to test measures and methodology that can be used clinically in a future Phase III clinical trial (e.g., localization, listening in noise, listening at soft levels).

Study Design

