A record of all adverse events will be kept. No formal statistical hypothesis will be tested. The primary safety endpoint will be 6 months post-implant. Adverse event information through 6 months post-implant will be summarized by event type, severity/seriousness, and whether related to the device and/or implant procedure.

Efficacy

The primary study objective is to obtain preliminary efficacy data in adults with asymmetric hearing loss who receive a CI in the poor hearing ear and maintain a HA in the better hearing ear. Efficacy is defined as post-implant improvement in the poor ear with a CI compared to pre-implant with a HA. Measures are sound field threshold levels and CNC monosyllabic words in quiet.

A secondary objective is to obtain efficacy data related to bimodal hearing. Efficacy is defined as post-implant improvement (CI in poor ear + HA in better ear) compared to the pre-implant best-aided condition (either HAs in both ears, or a HA in the better ear alone for adults with no aidable hearing in the poor ear). Measures are sound localization, speech recognition in noise, speech recognition at soft presentation levels, perceived hearing handicap, and reported quality of life.

Sample Size Justification

The primary efficacy endpoint is change in CNC performance from pre-implant to post-implant, with most of the gain expected to be achieved by 6 months. A clinically meaningful change on the CNC test is .10. In our past research we have found CNC standard deviations that range from .06 to .24. Assuming a correlation between repeated measures of .5 (typical in our work) these values translate into standardized mean differences (Cohen's *d*) ranging from .42 to 1.67. At the minimum effect size, a sample size of 37 is necessary for power of .80, the common standard (Cohen and Cohen, 1983; Keppel, 1991; Cohen, 1992). As indicated, the planned sample size will provide adequate to excellent power to detect clinically meaningful differences. Up to 40 participants will be enrolled to allow for attrition.

Note that the analyses described later will often be more complex than the simple approach used here for power calculations (a dependent means t-test), often involving change over longer periods of time, examining nonlinearity in the change profiles, and including additional predictors (e.g., patient characteristics). The impact of these modifications will generally be to increase power by including additional measures that

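### The safety evaluation is to use the degree of each adverse event, but the protocol's adverse event form list has only a yes/no seriousness item and no severity scale

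*Combined protocol and SAP*

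**What the plan says.** Secondary objective 2 (Study Objectives) and the Safety section make the same commitment: "The safety evaluation will be based on the number, type and degree of all adverse events". The Safety section then says that adverse event information through 6 months "summarized by event type, severity/seriousness, and whether related to the device and/or implant procedure". It also sets the status of this analysis: "No formal statistical hypothesis will be tested", and "The primary safety endpoint will be 6 months post-implant".

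Under Adverse Events, Investigator Responsibilities, the protocol states that entries on the Adverse Event CRF "will include the following information" and gives nine items: onset date, date reported, "Description of the AE", "Seriousness (yes or no", the investigator's assessment of the relationship to the device, the same for the procedure, treatment, outcome, and a combined relationship line that adds underlying disease.

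**The concern.** The objective and the planned summary name a quantity that the listed data items do not contain. Degree and severity describe how intense an event was. The yes/no item records whether the event met a seriousness criterion, which is a different question: a severe event can be non-serious.

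This matters because the events that the protocol itself singles out vary in degree. The Participant Interview Form asks about tinnitus, dizziness and the implant site. The consent risks include dizziness and postoperative discomfort. The definition of an adverse event covers worsening of an existing condition, and a tinnitus and dizziness baseline is taken before implantation. How much worse a symptom became is a question of degree.

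Because safety is not tested formally, the adverse event table is the safety result, and the trial is meant to inform a Phase III trial. A grade that is not recorded at the time cannot be reliably recovered afterwards.

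**Working it through.** No arithmetic applies, and the plan has no figure to reproduce. The check is whether each component of the planned safety summary has a matching item on the CRF list.

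| Component required (Study Objectives; Safety) | Matching item (Investigator Responsibilities) | Supported? |
|---|---|---|
| Number of events | One record per event | Yes |
| Event type | Free-text description | Yes |
| Seriousness | Yes/no flag | Yes |
| Relationship to device and to procedure | Two separate lines and the combined line | Yes |
| Degree or severity | None of the nine items | No |

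**Could seriousness stand in for degree?** The Serious Adverse Event section gives five criteria: death, threat to life, hospitalization beyond 24 hours or prolonged, permanent impairment or damage, and intervention to prevent that impairment or damage. They separate serious events from the rest but create no levels among the rest. Slight dizziness and dizziness that is disabling but transient and meets no criterion both receive a no. The commitment covers all adverse events, so it includes the non-serious ones.

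**Is a scale defined elsewhere?** The Adverse Events section defines an adverse event, a serious adverse event and an unanticipated adverse device effect, but no grade. The word severity otherwise refers to hearing loss (Introduction; Verification of Hearing Aids) or sits inside the quoted regulatory definition of an unanticipated adverse device effect.

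**Could another form supply it?** The Participant Interview Form is described as helping to identify events, with no mention of grading them. The contents of the Unanticipated Adverse Device Effect CRF and of the follow-up CRF are not listed.

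**What remains?** Description, treatment and outcome carry some information on degree. Each is written in the site's own terms, at three to four sites, with no shared scale.

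**The case against.** Five points can be made for the plan as it stands.

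- **The CRF itself is not in the documents.** The list is not stated to be exhaustive, and the protocol says that detailed information will be recorded. A reader might infer that the severity summary cannot be produced at all, or that severity goes uncaptured for every event. The documents do not support that: the form may hold a severity field, and three listed items bear on degree. What can be said is that the protocol specifies no graded item and no scale.
- **Severity and seriousness, joined by a slash, can be read as one classification.** On that reading the yes/no flag delivers the planned summary. The point stands for that one sentence, but it leaves degree without a matching item, and that word appears in both the objective and the Safety section.
- **Events are not recorded identically.** Treatment and outcome are noted, events are followed to resolution, and tinnitus and dizziness are queried before implantation, at initial stimulation and at each post-implant visit. This is correct. What is missing is a standardised grade, not all information about degree.
- **The stakes are small.** Safety is secondary and descriptive, enrolment is at most 40, and individual narratives are feasible. No power figure or efficacy estimate depends on a grade. This limits the importance of the point but does not remove the inconsistency.
- **The list is not padded.** A reader might take the combined relationship line as a duplicate that could make way for a severity item. It is not one: it is the only listed item that covers underlying disease.

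The documents give no adverse event rates, so no share of events that would fall in the non-serious class can be stated.

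**Conclusion.** The mismatch is real. Of the components that the safety evaluation names, number, type, seriousness and relatedness each have a listed item; degree does not, and no scale is defined. Followed as written, the protocol would let non-serious events be graded only by inference from unstandardised entries, so they could not be graded consistently across sites.

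The conclusion rests on the protocol's item list being what sites collect. If the form already has a severity field, the gap is in the protocol text and not in the data. In either case the effect is limited to the secondary, descriptive safety objective in a trial of 37 to 40 participants. The change is worth making because it is cheap and the information cannot be reliably recovered later. It is not a flaw that threatens the primary result.

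**What to change.** 1. Add one investigator-rated severity item to the Adverse Event CRF list under Investigator Responsibilities, with a defined scale. An example is mild, moderate or severe, with the worst severity of the event recorded.
2. Keep the combined relationship line, because it alone captures underlying disease.
3. In the Safety section, tabulate severity and seriousness separately.
4. If the form in use already has a severity field, list it and its scale in the protocol instead of adding one.

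Removing degree and severity from the objective and the summary would also restore consistency, but it would narrow a stated objective.

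The cost is one CRF field, updated on the follow-up CRF if the event worsens, and a short protocol amendment. Under Protocol Amendments, that needs approval by each site's IRB, and by FDA if the change is judged to affect participant safety or study validity. No visit or procedure is added.
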